# **5.2 Exclusion Criteria**

Subjects may not enter the study if they fulfill any of the following criteria:

1	Prior exposure to IACS 010750 or other exidative phosphorulation labilities
1.	Prior exposure to IACS-010759 or other oxidative phosphorylation Inhibitors.
2.	
 
Unstable cardiovascular function:
 
Symptomatic ischemia, or
 
Uncontrolled clinically significant conduction abnormalities (i.e., ventricular tachycardia on antiarrhythmic agents are excluded; 1st degree atrioventricular (AV) block or asymptomatic left anterior fascicular block/right bundle branch block (LAFB/RBBB) will not be excluded), or
 
Congestive heart failure (CHF) NYHA Class ≥ 3 (Appendix 9.5), or
 
Myocardial infarction (MI) within 6 months.
 
Left ventricular ejection fraction < 40 %.
 
Hypertension > 160 mm Hg systolic or > 100 mm Hg diastolic with or without antihypertensive therapy.
 

3.	Major surgery, other than diagnostic surgery, within 4 weeks prior to Day 1, without complete recovery from the surgical procedure
4.	Presence of $\geq$ CTCAE grade 2 toxicity (except alopecia or peripheral neuropathy) due to prior cancer therapy.
5.	Known positive for human immunodeficiency virus (HIV), hepatitis B virus surface antigen (HBsAg), or hepatitis C virus (HCV).
6.	Active uncontrolled infection. Infections controlled on concurrent anti-microbial agents are acceptable, and anti-microbial prophylaxis per institutional guidelines is acceptable.
7.	Participation in any other clinical trial involving another investigational agent for the treatment of AML within 2 weeks prior to day 1 of the study or at least 5 half-lives of the investigational agent, whichever is shorter.
8.	Lactate levels > 2 mmol/L and or and serum pH <7.35 at screening.
9.	Subject currently being treated with biguanides or other agents known to increase risk of lactic acidosis (reference Appendix 10.1).
10.	Subject has significant gastrointestinal abnormalities, including ulcerative colitis, chronic diarrhea associated with intestinal malabsorption, Crohn's disease, and/or prior surgical procedures affecting absorption or requirement for intravenous (IV) alimentation.
11.	Subjects with uncontrolled Type I or II diabetes mellitus
12.	Mental impairment that may compromise the ability to give informed consent and comply with the requirements of the study.
13.	Women who are breast-feeding or pregnant as evidenced by positive urine pregnancy test done within 72 hours of first dosing.
14.	Subject has a concurrent active malignancy under treatment, with the exception of: -Adequately treated carcinoma in situ of the breast or cervix uteri -Basal cell carcinoma of the skin or localized squamous cell carcinoma of the skin -Low-grade, early-stage prostate cancer with no requirement for therapy -Previous malignancy confined
15.	Acute promyelocytic leukemia.

IACS2015-001: Protocol Amendment #11 (01-21-20)

- 16. Any concomitant disease or condition that, in the clinical judgment of the treating physician, is likely to prevent the subject from complying with any aspect of the protocol or that may put the subject at unacceptable risk.
- 17. Subjects with  $\geq$  grade 1 peripheral neuropathy at screening.

### 6 Study Drug

### 6.1 Study Drug Administration

Cohorts 1 and 2: For each cycle 1, a single oral dose of IACS-010759 will be administered on day 1. The next dose of IAC-010759 will be administered on day 8, and daily continuously for the duration of the study with no interruptions unless there are adverse events as described in Section 4.1.9. IACS-010759 doses will be separated by intervals of approximately 24 hours (+/- 3 hours).

Cohorts 3-6 and Dose Expansion: Based on the observed accumulation of IACS-010759 throughout the dosing period in cohorts 1 and 2, a modified dosing regimen is being implemented, consisting of an induction phase in which IACS-010759 is administered daily for up to 7 days, followed by a maintenance phase in which a lower dose is administered weekly (or as otherwise specified by the SMC based on safety, PK and PD data observed) to maintain steady state plasma levels. Dosing will proceed on this schedule for the duration of the study with no interruptions unless there are adverse events as described in Section 4.1.9.

IACS-010759 will be administered without food, at least 1 hour before and at least 2 hours after eating. Each dose of IACS-010759 should be administered with 8 ounces of water. If a dose is missed, the next dose will not be increased to account for missing a dose. The subject will take the next regular dose at the scheduled time. Following cycle 1 (28-day cycle for cohorts 1 and 2, 21 day cycle for subsequent cohorts), subjects will receive one cycle of therapy every 21 days (+/- 4 days).

In cohorts 1 and 2, treatment was administered as an inpatient for 24 hours on day 1 and then starting on day 8 for the next 7 days for all enrolled subjects. In cohorts 3 and 4, treatment will be administered as an inpatient for 24 hours on Day 7 of Cycle 1 for all enrolled subjects. In subsequent cohorts, treatment will be administered as an inpatient for 24 hours on Day 5 of Cycle 1 for all enrolled subjects. IACS-010759 will be self-administered and subjects instructed not to dose on days when PK/PD samples are collected until advised by the research staff. Self-administration can occur on days without PK/PD and subjects will record administration in a provided diary.

In the expansion phase, after the first 6 subjects have been enrolled in the expansion cohort, the next 6 subjects will be enrolled in the Food Effect group where the effect of a high fat meal on the PK of IACS-010759 will be evaluated on day 1 of cycle 1 for the cohort (Food Effect group). The dose level to be administered will be the single agent RP2D induction dose as determined in the escalation phase or may be lower than the RP2D if clinical safety concerns prevent the use of RP2D for the food effect evaluation. Subjects in the Food Effect group will consume the high-fat meal within 30 minutes *prior to* IACS-010759 administration and blood samples collected at

the timepoints listed in the Study Flowchart for PK analysis. After this day 1 dose, subsequent doses of IACS-010759 will be administered without food as described above for the remainder of the cycle. The plasma levels in these subjects will be compared to those of the other subjects in the expansion cohort to determine whether consumption of a meal affects the plasma levels of IACS-010759.

### **6.2 Study Drug Information**

MDACC, IACS has defined a chemical synthesis process, specific purity profile and release specifications for the manufacture of IACS-010759. WuXi AppTec Co, Ltd. is producing GMP material on a 2.5 kg scale. The final drug product will be a dry filled capsule (DFC) formulation for oral administration.

Study drug will be packaged in 28-count bottles of 4 strengths: 0.1 mg, 0.5 mg, 1.0 mg and 5.0 mg, as described in Table 6. The first dose strength to be administered in cohort 1 of the dose escalation phase is 0.5 mg. Study drug may be stored at room temperature.

Table 6: IACS-010759 Drug Product Appearance by Strength

Strength	Appearance
0.1 mg	Hard Gelatin capsules, Size 3, white opaque cap, white opaque body
0.5 mg	Hard Gelatin capsules, Size 3, light green opaque cap, white opaque body
1.0 mg	Hard Gelatin capsules, Size 3, light blue opaque cap, white opaque body
5.0 mg	Hard Gelatin capsules, Size 3, dark blue opaque cap, white opaque body

The active ingredient in IACS-010579 is manufactured under GMP conditions by: Shanghai SynTheAll Pharmaceutical Co. Ltd., [name]

The finished drug product is manufactured under GMP conditions by: WuXi AppTec Co., Ltd, [name]

### 6.3 Drug Overdose Management

There are no known antidotes available for the IACS-010759. Any overdoses with this drug should be managed symptomatically.

## 7 Concurrent and Supportive Therapies

### 7.1 Non-Permitted Concomitant Therapies

Subject may not receive the following concomitant therapies during the study:

1.	Biguanides or other agents known to increase risk of lactic acidosis (Appendix 10.1)
2.	High dose steroids (>20 mg prednisolone or equivalent per day) including for GVHD
3.	Immunosuppressive drugs with the exception of cyclosporine and tacrolimus
4.	Erythropoietin and growth factors are not permitted to be used prophylactically in cycle 1 but allowed if needed in cycle 2 and onwards. However, these can be used therapeutically throughout the study.
5.	Other cancer therapy (chemotherapy, radiation or immunotherapy) other than the exceptions mentioned in Inclusion Criteria #9.
6.	Strong cytochrome P450 (CYP450) inhibitors or inducers, as specified below:

CYP Enzyme	Strong Inhibitors	Strong Inducers
CYP1A2	Ciprofloxacin, clinafloxacin, enoxacin, fluvoxamine, zafirlukast	
CYP2C8	Gemfibrozil	
CYP2C19	Fluconazole, fluvoxamine, ticlopidine	
СҮРЗА	Clarithromycin, conivaptan, grapefruit juice, itraconazole, ketoconazole, mibefradil, nefazodone, posaconazole, telithromycin, troleandomycin, voriconazole	Avasimibe, carbamazepine, phenobarbital, phenytoin, pioglitazone, rifbatun, rifampin, St. John's wort
CYP2D6	Bupropion, fluoxetine, paroxetine, quinidine	

### 7.2 Supportive Care Guidelines & Permitted Concomitant Therapies

### 7.2.1 Concomitant medication/therapies

In general, the use of any concomitant medication/therapies deemed necessary for subject supportive care and safety are permitted. Subjects with high WBC counts may receive hydroxyurea prior to study entry and during the first 2 cycles. Concurrent therapy for CNS prophylaxis or continuation of therapy for controlled CNS disease is permitted as defined in the inclusion criteria. With the exception of these agents, concomitant systemic chemotherapy is not permitted.

Concomitant medications are recommended as prophylaxis for nausea, vomiting, and infections, and are allowed for managing myelosuppression as shown in the table below. Concomitant medications will be recorded in the Case Report Form.

IACS2015-001: Protocol Amendment #11 (01-21-20) Page 47 of 59

Table 8: Instructions for the use of concomitant medications and therapies

Category of Use	Medication	Comment on Use	Restriction on Use
Recommended	Prophylactic antibiotics, antifungal agents, and antiviral agents.	Strongly encouraged	Agents known to increase risk of lactic acidosis (see Appendix 10.1)
	Antiemetic agents	According to standard of care at MDACC	None
Allowed	Oral allopurinol or rasburicase	At investigators discretion	None
	Leukapheresis	According to standard of care at MDACC	Before induction 1 day 1 only
	Red blood cell transfusion	None	None
	Platelet transfusion	None	None
	White blood cell transfusion	At investigators discretion according to standard of care at MDACC	None
	Myeloid growth factors or platelet growth factor	At investigators discretion according to standard of care at MDACC	None
	Erythropoietin or darbepoetin	At investigators discretion according to the standard of care at MDACC	None
	Any other medication for supportive care	At investigators discretion according to standard of care at MDACC	Agents known to increase risk of lactic acidosis (see Appendix 10.1)

### 7.2.2 Use of Blood Products

During the administration of IACS, subjects may receive red blood cell (RBC) or platelet transfusions, if clinically indicated, per institutional guidelines.

Myelosuppression is expected in subjects with AML due to underlying disease. Most subjects will have neutropenia, thrombocytopenia, or both at study entry. Significant or life-threatening myelosuppression may be managed with growth factor support including G-CSF, GM-CSF and platelet growth factors and erythropoietin/darbopoietin/blood transfusion according to institutional standard of care, American Society of Clinical Oncology (ASCO) Practice Guidelines, and/or NCCN Practice Guidelines.

### 7.2.3 Lactic Acidosis and Severe Acidemia Management

Subjects with lactic acidosis and severe acidemia (pH < 7.1) should be seen by a nephrology specialist as soon as possible and receive bicarbonate therapy. When using bicarbonate therapy in subjects with lactic acidosis and severe acidemia, the aim is to maintain the arterial pH above 7.1. Rapid infusions of sodium bicarbonate may increase the pCO2, accelerate the production of lactate, lower the ionized calcium, expand the extracellular space, and raise the serum sodium concentration. There is little evidence that any alternative buffering agents are superior to bicarbonate therapy. In adequately ventilated subjects with lactic acidosis and severe acidemia, 1 to 2 mEq/kg sodium bicarbonate is given as an intravenous bolus. This dose is repeated after 30 to 60 minutes if the pH is still below 7.1.

### 8 Administrative, Legal & Ethical Requirements

### 8.1 Adverse Event, serious adverse event and reporting

### 8.1.1 Adverse Event (AE):

Any untoward medical occurrence in a subject or clinical investigation subject administered an investigational product. An AE does not necessarily have a causal relationship with the medicinal product.

The criteria for identifying AEs are:

- Any unfavorable and unintended sign (including an abnormal laboratory finding), symptom, or disease temporally associated with the use of a medicinal product, whether or not considered related to the medicinal product
- Any new disease or exacerbation of an existing disease
- Any deterioration in non-protocol-required measurements of laboratory value or other clinical test (e.g., ECG or X-ray) that results in symptoms, a change in treatment, or discontinuation from study drug
- Recurrence of an intermittent medical condition (e.g. headache) not present at Baseline.

An abnormal laboratory test result may be considered as an adverse event if the identified laboratory abnormality leads to any type of intervention whether prescribed in the protocol or not.

A laboratory result should be considered by the Investigator to be an adverse event if it:

- Results in the withdrawal of study treatment
- Results in withholding of study treatment pending some investigational outcome
- Medical evaluation, results in the initiation of an intervention (e.g. potassium supplement for hypokalemia)
- Any out of range laboratory value that in the Investigator's judgment, fulfills the definitions of an AE with regards to subject's medical profile
- Increases in severity compared to Baseline by ≥ 2 NCI grades (see Appendix C for NCI CTCAE Ver 4.03 criteria), with the exception of lymphocytes, albumin, cholesterol, glucose and phosphate. For these tests, a change of ≥ 2 grades will be evaluated by the Investigator to determine if they are of clinical significance and if so, will be considered an adverse event.

IACS2015-001: Protocol Amendment #11 (01-21-20) Page 49 of 59

Abnormal laboratory values should not be listed as separate AEs if they are considered to be part of the clinical syndrome that is being reported as an AE. Any laboratory abnormality considered to constitute an adverse event should be reported on the Adverse Event Case Report Form (CRF).

It is the responsibility of the Investigator to review all laboratory findings, including laboratory assessments performed at outside labs, in all subjects and determine if they constitute an adverse event. Medical and scientific judgment should be exercised in deciding whether an isolated laboratory abnormality should be classified as an adverse event. The Investigator will assess external laboratory findings and determine clinical significance of any which are deemed adverse events. In these instances, the laboratory reports should be signed and dated by the Investigator.

### **8.1.2** Reporting of Adverse Events

Adverse events will be recorded by the research personnel on the CRF. The Investigator or physician designee is responsible for verifying and providing source documentation for all adverse events and assigning the attribution for each event for all subjects enrolled on the trial.

For this protocol, adverse events and protocol specific data will be entered into the electronic case report form. Serious adverse events will be entered into ARISg and reconciled against the clinical data base at the end of the study. All AEs encountered during the clinical study will be reported on the CRF. All AEs, regardless of relationship to study drug or procedure, should be collected, beginning from the time of the first protocol-specific intervention (study drug administration). New information regarding signs and symptoms that occurred prior to the first study medication dose on Day 1 should be recorded under the subject's Medical History. Adverse events in clinical investigation subjects include any change in the subject's condition. This includes symptoms, physical findings, or clinical syndromes.

Subjects with AEs that are ongoing at the subject's last study visit must be followed until resolution or for 30 days after the subject's last study visit, whichever comes first. Adverse events that are reported during the Follow-up Period will be recorded on the Adverse Events CRF and followed until resolution or for up to the 30 days after the subject's last study visit, whichever comes first, with the exception that SAEs will be followed until the event resolves or the event or sequelae stabilize.

Every effort must be made by the Investigator to categorize each AE according to its severity and its relationship to the study treatment.

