Limited PK data from subjects in cohorts 1 and 2 showed unexpected levels of accumulation of IACS-010759 throughout the dosing period, consistent with a model in which the clearance of IACS-010759 decreases exponentially with time, leading to an increasingly long terminal  $T_{1/2}$  and accumulation upon multiple dosing. A mathematical model and simulation has been developed based on data from the subjects treated with IACS-010759 to date that predicts the observed human PK. Based on this model, a modified dosing regimen is being implemented for the dose escalation phase with cohorts 3-6 and for the dose expansion phase with cohort 7, consisting of an induction phase in which IACS-010759 is administered daily for up to 7 days, followed by a maintenance phase in which a lower dose is administered weekly to maintain steady state plasma levels (or as otherwise specified by the SMC based on safety, PK and PD data observed).

Page 17 of 59

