#### 4.1.15 Follow-Up at Treatment Discontinuation or Early Withdrawal

Subjects who discontinue treatment for any reason should complete end-of-treatment procedures when possible. End of treatment procedures will include a physical examination, CBC with differential and platelets and chemistry. A bone marrow aspiration may be recommended only if non-response or progressive disease cannot be unequivocally diagnosed from peripheral blood. Although treatment will be discontinued at that time, all subjects who do not die, withdraw consent for follow-up, or become lost to follow-up, will remain on study for

follow-up evaluations. Subject will be followed for possible delayed emergence of IACS-010759 related toxicity at least 30 days after the last protocol treatment. Subjects who discontinue the study will be requested to return for additional PK and/or PD blood daws, approximately every 4 days, when possible, for up to 4 weeks after the last study drug administration to further explore the PK and PD activity of IACS-010759 following discontinuation of study drug. The 30-day (+/-7 days) follow-up visit will be scheduled as a clinic visit for clinical evaluation and physical examinations. If the subject cannot make it to the site for this visit, the required follow up treatment procedures may be performed by a local physician and the records forwarded to the site. The research nurse will also contact the subject by telephone and obtain a verbal assessment of the subject's condition. The phone conversation will then be documented in the subject's charts.

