## Cohorts 3-4 Dose-Escalation

Conorts 5-4 Dose-Escalation	Screen					Cycle 21 da							Cycle 2 21 day:			Сус (21 с		Addition Cyclo (21 da	es	End of Study or Early Termination
Study Day	-7 to -1	1+	2	4	7*	8	12	15	17	21	22	29	36	37	42	43	63	Every 2	1 days	30 after last Dose
Name of Cycle Day		C1 D1	C1 D2	C1 D4	C1 D7	C1 D8	C1 D12	C1 D15	C1 D17	C1 D21	C2 D1	C2 D8	C2 D15	C2 D16	C2 D21	C3 D1	C3 D21	CX D20	CX D21	51
+/- days allowable				1	1	1	1	1	2	+2	1	1	1	2	1	3	3	4	4	7
Study Drug§		I	NDU	CTIOI	V								М	AINTE	NANC	E				
Study Drugg		Х	Х	Х	Х	Х		Х			Х	Х	Х			Х				
Disease Assessment																				
Bone marrow aspirate and/or biopsy¥	х									х							Х	Every 2-3 cycle		x
Overall Response Rate ‡										Х							Х		Χ‡	Х
Study Procedures & Examinations																				
Eligibility Assessment & Informed Consent	Х																			
Demographics A	Х																			
Medical history B	Х																			
MUGA/ECHO	Х																			
Dilated eye exam with fundus photos N		Х																		
Neurology review and exam 		Х																		
12-lead ECG (QTcF)	Х	X 			X 			X 		Х										
Phys. Exam (inc. weight)	Х	Х			Х			Х		Х	Х				Х	Х	Х		Х	Х
ECOG	Х	Х									Х					Х			Х	Х
Vital Signs (Temp., HR, BP, RR)	Х	X 	X 	X 	X 	X 	Х	X 		Χ	X 	X 	X 	Х	Х	X 	Х		Х	X
Concomitant Medication C	Х	Х	Χ	Х	Х	Х	Χ	Х	Х	Χ	Х	Х	Χ	Х	Х	Х	Х		Χ	X
Adverse Events D		Х	Х	Х	Х	Х	Х	Х	Х	Х	Х	Х	Х	Х	X	Х	Х		Х	X
Labs																				
Pregnancy test	X																			
Blood Hematology E, I, J	Х	X 			X 	X 	Х	X 	Х	Х	Х			Х	Х	Х	Х		Х	X
Chemistry F, I	Х	X 			X 	X 	Х	X 	Х	Х	Х	X 	X 	Х	Х	Х	Х		Х	X
Coagulation, lipase, amylase & urinalysis G, I	Х	X 			X 	X 	Х	X 	Х	Х	Х	X 	X 	Х	Х				Х	Х
Lactate and blood pH I, K	Х	X 	X 	X 	X 	X 	Х	X 	Х	Х	X 	X 	X 	Х	Х	X 	Х		Х	Х
Research Labs																				

Blood collection- pharmacodynamics H	X	X 			X 			X 		Χ									$X^L$

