### Adverse events (AE) related to study conditions

The serious adverse event (SAE) reporting period will begin with the time of the first protocol-specific intervention (study drug administration) Regardless of severity or seriousness, new information regarding signs and symptoms that occurred prior to the first study medication dose on Day 1 should be recorded under the subject's Medical History.

AEs should be followed to resolution or stabilization, and reported as SAEs if they become serious. This also applies to subjects experiencing AEs that cause interruption or discontinuation of investigational product, or those experiencing AEs that are present at the end of their participation in the study. Such subjects should receive post-treatment follow-up as appropriate.

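### Two sections give different stop rules for non-serious adverse events still ongoing at the end of participation, and the 30-day visit window lets the last scheduled check fall on day 23

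*Combined protocol and SAP*

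**What the plan says.** Four places in the protocol bear on when AE follow-up ends.

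- **8.1.2, Reporting of Adverse Events.** AEs ongoing at the last study visit "must be followed until resolution or for 30 days after the subject's last study visit, whichever comes first". AEs reported in the follow-up period have the same 30-day limit, "with the exception that SAEs will be followed until the event resolves or the event or sequelae stabilize".
- **8.1.6, under Adverse events (AE) related to study conditions.** "AEs should be followed to resolution or stabilization, and reported as SAEs if they become serious". The next sentence extends this to AEs that cause interruption or discontinuation of study drug and to AEs still present when participation ends. There is no time limit.
- **4.1.15, Follow-Up at Treatment Discontinuation or Early Withdrawal.** "Subject will be followed for possible delayed emergence of IACS-010759 related toxicity at least 30 days after the last protocol treatment". The same paragraph then says: "The 30-day (+/-7 days) follow-up visit will be scheduled as a clinic visit for clinical evaluation and physical examinations". All three flowcharts in 4.2 place the End of Study visit at "30 after last Dose" with 7 days allowed, and this is the last column in which the AE row is marked.
- **8.1.7, Serious Adverse Event Reporting.** Serious AEs are captured to 30 days after the last dose, and related ones remain reportable after that.

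No section gives an end date for collecting new non-serious AEs. Section 4.3.2 defines a treatment-emergent AE by onset or worsening after dosing and tabulates these events by maximum severity and relationship. It gives no end date either.

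**The concern.** A site holding an unresolved non-serious AE at the last visit has two instructions. One closes the record 30 days later whatever the state of the event, and the other keeps it open until the event resolves or stabilizes. The recorded end date, the outcome and possibly the maximum grade then depend on which section was read.

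This matters more here than in many phase 1 trials, for three reasons. Safety and tolerability is the primary objective. Section 3.1 describes a model in which "the clearance of IACS-010759 decreases exponentially with time, leading to an increasingly long terminal" half-life and accumulation result, so exposure may outlast dosing. Dilated eye and neurology examinations were added on the Safety Monitoring Committee's recommendation, but the flowcharts schedule them at baseline only. Ordinary AE follow-up is therefore the main route for learning whether a non-serious neuropathy or visual change worsens or recovers. Section 8.1.4 also uses the course of an event after stopping drug when judging relatedness, so truncated follow-up can affect attribution.

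**Working it through.** The plan states no figure on this point to reproduce. The check is day arithmetic plus a comparison of the rules.

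**1. Visit window.** Inputs: nominal day 30 after last dose and tolerance of 7 days (4.1.15 and flowcharts).
- Earliest: 30 − 7 = day 23. Latest: 30 + 7 = day 37.
- Shortfall against the requirement in 4.1.15: 30 − 23 = 7 days, and 7/30 = 23% of the period.

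**2. Closure under 8.1.2.** Input: 30 days after the last study visit. If that visit is the 30-day visit:
- 23 + 30 = day 53
- 30 + 30 = day 60
- 37 + 30 = day 67

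The last study visit is not defined. If it means the last on-treatment visit, closure comes earlier.

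**3. Closure under 8.1.6.** Resolution or stabilization, with no day limit.

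**4. The same event under both rules.** Take a hypothetical grade 2 non-serious AE that led to dose interruption. It is ongoing at a day-30 visit and worsens to a non-serious grade 3 after day 60.
- 8.1.2: closed on day 60, maximum grade 2, unresolved.
- 8.1.6: still open unless it had been judged stable, so maximum grade 3.

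If the event had been judged stable before day 60, 8.1.6 would allow closure sooner than 8.1.2. The rules differ, but neither is always the longer.

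**5. Starting points.** The clock runs from last protocol treatment in 4.1.15, from last dose in the flowcharts and 8.1.7, and from last study visit in 8.1.2.

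**6. What does not depend on these rules.**
- Incidence of an ongoing AE: it is already recorded and counted at onset (4.3.2).
- Serious AEs: exempt from the cap in 8.1.2, followed to recovery or stabilization in 8.1.7, and reportable after day 30 if related. Section 8.1.3 makes every grade 4 or 5 AE serious.
- DLT counts and stopping: 4.1.10 ties DLTs to the first cycle, with a separate day-42 clock for myelosuppression. The boundaries in Table 3 (4 of 12, 6 of 18) use only DLT counts. As a check, the early-stopping probabilities in Table 4 are reproduced by P(X ≥ 4), X binomial with n = 12: 0.0256, 0.0922, 0.2054, 0.3512 and 0.5075 for true rates 0.10 to 0.30. No AE end date enters.

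**The case against.** The strongest reply is that this is a wording matter with little reach, and much of that reply stands.

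- **A reader might infer that follow-up stops on day 23.** It does not. Day 23 is the earliest date of one clinic visit. The 30-day minimum in 4.1.15 still applies, the paragraph adds telephone contact and optional PK/PD draws for up to 4 weeks, and an AE ongoing at a day-23 visit is followed to day 53 under 8.1.2 unless it resolves. What remains is that no scheduled assessment need cover the last 7 days, and the telephone contact has no stated date.
- **A reader might infer that persistent toxicity is counted under one rule and lost under the other.** It is not. The event is already in the incidence table. Only later worsening, outcome and duration can differ.
- **A reader might infer that the MTD or RP2D rests on the disputed rules.** The 3+3 and expansion rules use DLT counts. Section 4.1.7 has its own provisions for later toxicity: a planned-dose check after 4 cycles, and case-by-case review of late-onset DLTs that can revise the MTD. The link to dose selection is therefore indirect.
- **The difference might be an intended split by seriousness.** That explains the exemption in 8.1.2. It does not explain 8.1.6, which speaks of AEs generally and of their being reported as serious only if they become so.
- **8.1.6 need not mean longer follow-up**, because stabilization also closes an event. This is correct, and it limits what can be said about the direction of the effect. It does not remove the contradiction.

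**Conclusion.** The point holds in a limited form. Sections 8.1.2 and 8.1.6 contradict each other for non-serious AEs ongoing at the end of participation. The visit window also conflicts with the 30-day minimum in its own paragraph.

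The exposed information is non-serious worsening after about day 53 to 67 (assuming the last study visit is the 30-day visit), outcome and duration of ongoing AEs, and new non-serious AEs from day 24 onward when the final visit is early.

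The only size that the documents support is the scheduling gap of up to 7 of 30 days. They give no times to resolution, so the share of AEs cut off cannot be derived. Under an assumed exponential time to resolution from last dose, the share unresolved at day 60 is 2^(−60/median): 0.25, 0.50 or 0.71 for assumed medians of 30, 60 or 120 days. That range is too wide to serve as an estimate. It also ignores death as a competing event, although 2.1 cites a median survival of 3.8 months in refractory disease, and an unresolved AE is not a miscounted one. The contradiction is certain. The size of its effect on the safety tables is not known.

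**What to change.** 1. Change the follow-up visit window from ±7 to 0/+7 days in 4.1.15 and in all three flowcharts. The visit then falls on days 30 to 37.
2. Reconcile 8.1.2 with 8.1.6 so that both state one rule counted from the last dose. AEs that are study-drug-related, or that led to interruption or discontinuation, are followed to resolution or stabilization, as 8.1.6 already says.
3. If a time limit is kept for the remaining unrelated non-serious AEs, write it identically in both sections. The present nominal limit is 30 + 30 = 60 days after last dose, so replacing only the words for the starting point would shorten it to 30.
4. State that new AEs of any seriousness are collected through at least 30 days after the last dose.

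The cost is wording, a slightly later visit for some subjects, and a few extra phone contacts or record requests. No new procedure is added. For the same reason, the change will not by itself show whether eye or nerve findings reverse, since those examinations remain baseline only.
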